6.2.1. Preparation and Dispensing

Refer to the IP manual for instructions on how to prepare the investigational product for administration. Investigational product should be prepared and dispensed by an appropriately qualified and experienced member of the study staff (eg, physician, nurse, physician's assistant, nurse practitioner, pharmacy assistant/technician, or pharmacist) as allowed by local, state, and institutional guidance.

Investigational product and placebo will be prepared by qualified unblinded site personnel according to the IP manual. The investigational product will be administered to maternal blinded participants.

6.3. Measures to Minimize Bias: Randomization and Blinding

6.3.1. Blinding of Study Site Personnel

This is an observer-blinded study, as the physical appearance of the RSV vaccine and placebo may differ.

The maternal participant, investigator, study coordinator, and other site staff will be blinded. At the study site, only the dispenser(s)/administrator(s) are unblinded.

Contact between the unblinded dispenser(s)/administrator(s) and maternal participants should be kept to a minimum. The investigator, study coordinator, and any site staff other than the unblinded dispenser(s)/administrator(s) must not be allowed to know the investigational product assigned to any maternal participant and must not be allowed to see the investigational product.

6.3.2. Blinding of the Sponsor

The sponsor study team members will be blinded until the first planned analysis event (see [Section 9.5.1](#)).

Laboratory personnel performing the serology and virology assays will remain blinded to vaccine assigned/received throughout the study.

Certain sponsor personnel not directly involved in the conduct of the study will review unblinded data as defined in the IRC charter. Unblinded sponsor personnel who are not part of the study team will be assigned to assess whether a stopping rule is triggered and to conduct ongoing safety review.

Those study team members who are involved in ensuring that protocol requirements for investigational product handling, allocation, and administration are fulfilled at the site (eg, study manager, clinical research associates) will be unblinded for the duration of the study.

6.3.3. Allocation to Investigational Product

Allocation of maternal participants to vaccine groups will proceed through the use of an interactive response technology (IRT) system (interactive Web-based response [IWR]). The site personnel (study coordinator or specified designee) will be required to enter or select information including but not limited to the user's identification (ID) and password, the protocol number, and the maternal participant number. The site personnel will then be provided with a vaccine assignment, randomization number, and dispensable unit (DU) or container number as investigational product is being supplied via the IRT system. The IRT system will provide a confirmation report containing the maternal participant number, randomization number, and DU or container number assigned. The confirmation report must be stored in the site's files.

Investigational product will be dispensed at the study visits summarized in the [SoA](#).

The study-specific IRT reference manual and IP manual will provide the contact information and further details on the use of the IRT system.

Maternal participants will be assigned to receive investigational product according to the randomization scheme. Investigators will remain blinded to each maternal participant's assigned investigational product throughout the course of the study. In order to maintain this blind, an otherwise uninvolved third party will be responsible for the preparation and

dispensing of all investigational product and will endeavor to ensure that there are no differences in time taken to dispense or visual presentation following randomization.

In the event of a Quality Assurance audit, the auditor(s) will be allowed access to unblinded investigational product records at the site(s) to verify that randomization/dispensing has been done accurately.

Maternal participants will be allocated to a vaccine group as described above. The infants of the maternal participants will be assigned an infant participant number at birth.

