1.3.1. Schedule of Activities for Maternal Participants

Visit Description	Screening (Visit 0)	Vaccination	2-Week Follow-up Visit	1-Month Follow-up Visit	Delivery	1-Month Postdelivery Visit	6-Month Postdelivery Visit	12-Month Postdelivery Visit
Visit Window (Days)	Day -14 to Day -2 Prior to Vaccination ^a	Day 1	14 to 17 Days After Vaccination ^b	28 to 42 Days After Vaccination ^b	Varies	28 to 35 Days After Delivery	168 to 210 Days After Delivery	350 to 378 Days After Delivery
Informed consent	X							
Assign single maternal participant identifier	X							
Demography	X							
Record current alcohol, tobacco, and marijuana usage	X							
Medical history including obstetric history ^c	X							
Record LMP and EDD	X							
Vital signs ^d	X	X	X	X				
Physical examination	X							
Measure weight and height	X							
Measure weight		X	X	X				
Obstetric examination	X	X	X	X				
Record baseline concomitant medication	X							
Record details of any antenatal steroid treatment, monoclonal antibodies, blood transfusions, or Rho(D) immune globulin	X	X	X	X	X	X	X	X
Record nonstudy vaccine information	X	X	X	X	X	X	X	X
Review eligibility criteria	X							
Blood draw for hematology and blood chemistry assessments	X							
Review laboratory results for hematology and chemistry assessments ^e		X						
Blood draw for HBV, HCV, HIV, and syphilis testing	X							
Review results from HBV, HCV, HIV, and syphilis testing ^e		X						
Review temporary delay criteria		X						
Review continued eligibility		X	X	X	X			
Blood draw for serologic assessment (~25 mL per blood sample)		X	X	X	X		X	

Visit Description	Screening (Visit 0)	Vaccination	2-Week Follow-up Visit	1-Month Follow-up Visit	Delivery	1-Month Postdelivery Visit	6-Month Postdelivery Visit	12-Month Postdelivery Visit
Visit Window (Days)	Day -14 to Day -2 Prior to Vaccination ^a	Day 1	14 to 17 Days After Vaccination ^b	28 to 42 Days After Vaccination ^b	Varies	28 to 35 Days After Delivery	168 to 210 Days After Delivery	350 to 378 Days After Delivery
Urine sample for glucose and protein testing	X	X						
Assign randomization and container number		X						
Administer investigational product		X						
Postvaccination observation ^f and assessment of immediate adverse events		X						
Dispense e-diary, digital thermometer, and measuring device ^g		X						
Review and/or collect e-diary ^h			X					
Record pregnancy outcome information					X			
Record concomitant medication taken to treat an adverse event		X	X	X	X	X	X	X

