6.3.4. Breaking the Blind

At the initiation of the study, the investigator will be instructed on the method for breaking the blind for an individual participant. The method will be an electronic process. Blinding codes should be broken only in exceptional circumstances when knowledge of the actual treatment code is absolutely essential for further management of the participant.

Investigators are encouraged to discuss with a member of the study team if they believe that unblinding is necessary. When the blinding code is broken, the reason must be fully documented and entered on the CRF.

The study-specific IRT reference manual and IP manual will provide the contact information and further details on the use of the IRT system.

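### Does Protocol Section 6.3.3 hand the blinded study coordinator the participant's vaccine group?

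*Protocol*

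**What the plan says.** Section 6.3.3 (Allocation to Investigational Product) first names who operates the IRT: "The site personnel (study coordinator or specified designee) will be required to enter or select information". It then says what comes back: "The site personnel will then be provided with a vaccine assignment, randomization number, and dispensable unit (DU) or container number". The next sentence describes the record kept on file: "The IRT system will provide a confirmation report containing the maternal participant number, randomization number, and DU or container number assigned". Later the section says that investigators stay blinded throughout, and that someone not otherwise involved prepares and dispenses product to protect the blind.

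Section 6.3.1 (Blinding of Study Site Personnel) sets the rule for the site: "The maternal participant, investigator, study coordinator, and other site staff will be blinded". The exception is narrow: "At the study site, only the dispenser(s)/administrator(s) are unblinded". Everyone else at the site, with the coordinator named, "must not be allowed to know the investigational product assigned to any maternal participant", nor may they see it.

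Three other places bear on the point:

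- The maternal schedule of activities (Section 1.3.1) describes the step as "Assign randomization and container number".
- Section 8.10.1.2 (Vaccination, Day 1) has staff obtain the randomization number and kit number from the IRT, with the infant blood sampling schedule supplied at the same time. It allows blinded or unblinded staff to do this.
- Section 6.3.4 (Breaking the Blind) says: "Blinding codes should be broken only in exceptional circumstances when knowledge of the actual treatment code is absolutely essential". It makes this a distinct electronic process with a documented reason.

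Neither the protocol nor the SAP defines the term *vaccine assignment* as used in Section 6.3.3.

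**The concern.** The coordinator appears in both sections: as the first-named IRT user in 6.3.3, and as a blinded person in 6.3.1. Section 6.3.3 lists the vaccine assignment as an item separate from the randomization and container numbers. Those two numbers are already enough to pick the right carton, so the third item is easily read as the product itself. The section's own reassurance about blinding names investigators only, not the coordinator.

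A real leak here would matter. The study is observer-blinded because vaccine and placebo may look different, so the site blind rests on limiting who sees and knows the product. The primary endpoints are safety endpoints. Blinded staff watch for acute reactions after injection, and investigators judge whether adverse events are related, which feeds several stopping rules in Section 8.2.5. A coordinator who knew the arm could influence how events are elicited, recorded or attributed.

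**Working it through.** No arithmetic applies beyond a count. The check is whether the sections can all be followed at once, and on which reading.

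**Step 1. What the IRT step yields, place by place.**

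| Place | Items named | Vaccine assignment named? |
|---|---|---|
| 6.3.3, IRT output sentence | vaccine assignment, randomization number, DU or container number | Yes |
| 6.3.3, confirmation report | participant number, randomization number, DU or container number | No |
| 1.3.1, schedule row | randomization and container number | No |
| 8.10.1.2, Day 1 steps | randomization number, kit number, infant sampling schedule | No |

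One of four mentions a vaccine assignment; 4 − 1 = 3 do not. The count should not be pressed. The first two rows are neighbouring sentences, the report is a filed record, and the schedule row is a short label. It shows which phrase is out of line and says nothing about harm.

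**Step 2. Test each reading of the phrase.**

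*Reading A: the IRT displays the named arm to whoever logs in.* Section 6.3.1 would be breached whenever a coordinator randomized someone. The permission in 8.10.1.2 for blinded staff to use the IRT would be self-defeating. The restricted code-break in 6.3.4 would serve little purpose at the site, and so would separate third-party dispensing.

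*Reading B: the assignment is made by the system and reaches a blinded user only in masked form, through the randomization and container numbers or a code.* Sections 6.3.1, 6.3.3, 6.3.4, 8.10.1.2 and the schedule can all be followed together.

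*Reading C: the arm is displayed, but only to an unblinded dispenser or administrator acting as the designee.* Section 6.3.1 is again satisfied, because that person is already within its exception. This reading fits less well with the coordinator being named first.

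Reading A defeats several other provisions. Reading B defeats none, and Reading C keeps the blind.

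**Step 3. Which text governs conduct.** Section 6.3.1 is the specific rule on site blinding and is phrased as a prohibition. Section 8.10.1.2 is the instruction staff follow on the day. Both point the same way. Sections 6.3.3 and 8.10.1.2 refer to the IRT manual for detail. That manual is not among the documents reviewed, so the display settings themselves cannot be checked here.

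**Step 4. Reach into the analysis.** The SAP defines the randomized population by assignment of a randomization number in the IRT. Safety is analysed by product received and immunogenicity by product randomized (SAP Section 4). None of this depends on what the IRT user sees. Serology laboratory staff stay blinded throughout (Section 6.3.2), and e-diary reactions are recorded by the blinded participant. Nothing in the documents allows a bias to be quantified.

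**The case for a change.** The strongest case for a change runs as follows. Section 6.3.2 uses very similar words, vaccine assigned or received, for the information laboratory staff must not have. Section 9.5.2 treats access to randomization assignments as the thing withheld from the sponsor. On the protocol's own usage, then, a vaccine assignment sounds like the concealed fact rather than a code. Section 8.10.1.2 expressly expects blinded IRT users, so it cannot be assumed that the designee is always unblinded. A manual does not cure a conflict between two protocol sections. Clear intent makes the edit easy; it does not make the wording consistent.

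Much of this stands. The phrase is there, no masking statement accompanies it, and read alone it suggests the arm. What does not follow is a contradiction that someone must resolve before the trial can run as designed. The provisions that show which phrase is out of line also tell a site how to act: the coordinator may not know the product, and blinded staff obtain numbers. A reader would have to set aside an outright prohibition and the Day 1 instruction to conclude that a blinded coordinator should be shown the arm. Deleting the phrase or adding the word masked would be tidy, but it would restate what Section 6.3.1 already requires.

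**Conclusion.** The concern does not call for a change. Section 6.3.3 contains one imprecise phrase, an ambiguity against Section 6.3.1 rather than a demonstrated conflict, and the rest of the protocol resolves it in favour of a masked output. Its size is one phrase in one of four descriptions of the randomization step. No unblinding is shown, and no effect on any endpoint, interval or analysis population follows from the wording.

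This rests on two assumptions: that sites read Section 6.3.3 together with Sections 6.3.1 and 8.10.1.2, and that the IRT was configured to match them. The documents support the first. The second lies in the IRT manual and system settings, which were not available. If the system did display the arm to blinded users, that would be a failure to carry out Section 6.3.1, and the plan as written already forbids it.

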6.3.4. Breaking the Blind

At the initiation of the study, the investigator will be instructed on the method for breaking the blind for an individual participant. The method will be an electronic process. Blinding codes should be broken only in exceptional circumstances when knowledge of the actual treatment code is absolutely essential for further management of the participant.

Investigators are encouraged to discuss with a member of the study team if they believe that unblinding is necessary. When the blinding code is broken, the reason must be fully documented and entered on the CRF.

The study-specific IRT reference manual and IP manual will provide the contact information and further details on the use of the IRT system.

6.4. Study Intervention Compliance

All doses of investigational product will be administered by the appropriately designated study staff at the investigator site.

6.5. Concomitant Therapy

6.5.1. Prohibited Concomitant Treatments – Maternal Participants

- Investigational vaccines, drugs, or medical devices are prohibited during the course of the study.
- Blood/plasma products or immunoglobulins (except Rho(D) immune globulin [eg, RhoGam], which can be given at any time) and immunosuppressive therapy are prohibited during the course of the study.
- Nonstudy vaccines may not be given concomitantly with the investigational product or within 6 days after investigational product administration (Day 1 to Day 7), except if medically necessary (eg, during an outbreak or pandemic situation).

6.5.2. Permitted Concomitant Treatments – Maternal Participants

- Licensed vaccines (including influenza and tetanus, diphtheria, and acellular pertussis vaccine [Tdap]) may be given during the study starting 7 days after investigational product administration (Day 8) as per local recommendation for immunization in

pregnant women. If medically necessary (eg, pandemic), influenza vaccine, Tdap, or other vaccines may be given at any time.

- Inhaled/nebulized, intra-articular, intrabursal, or topical (skin or eyes) corticosteroids are permitted.
- The use of antipyretics and other pain medication to treat symptoms associated with investigational product administration is permitted during participant participation in the study.
- The use of prophylactic antipyretic medication, while permitted, is not recommended on the day prior to vaccination or the day of the investigational product administration.

6.5.3. Recording Nonstudy Vaccinations and Concomitant Medications – Maternal Participants

Details of any medications taken at enrollment will be collected and recorded in the CRF. Medication taken to treat AEs from the signing of the ICD until 1 month after vaccination will be recorded in the CRF. In addition, any medication to treat MAEs or SAEs from 1 month after vaccination until the final study visit will be recorded in the CRF.

Details of any vaccinations given at any time during the pregnancy until the final study visit will be collected and recorded in the CRF.

Details of any antenatal steroid treatment, monoclonal antibodies, blood transfusions (eg, whole blood, packed cells), or Rho(D) immune globulin (eg, RhoGam) given to the maternal participant at any time during the pregnancy or during the study will be collected and recorded in the CRF.

6.5.4. Permitted Concomitant Treatments – Infant Participants

- Routine treatments (including vaccinations) and routine procedures (eg, circumcision) are permitted at any time according to national recommendations or medical standard of care or accepted practice.
- Prescription and nonprescription medications, vitamins, minerals, and herbal remedies are permitted during infant participant participation in the study.
- Local anesthetic may be applied to the site of the blood draw, as appropriate.

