5.2.2. Exclusion Criteria – Infant Participants

1. Infant who is a direct descendant (eg, child or grandchild) of the study personnel.

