6.5.5. Recording Nonstudy Vaccinations and Concomitant Medications – Infant Participants

Details of any vaccinations, monoclonal antibodies (eg, Synagis), or blood transfusions (eg, whole blood, packed cells) given to the infant participant will be collected from the time of birth until the final study visit and recorded in the CRF.

Details of any medication taken to treat AEs from the time of birth until Visit 2 will be recorded in the CRF. In addition, any medication taken to treat AEs of special interest, MAEs, or SAEs from Visit 2 until the final study visit will be recorded in the CRF.

CCI

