2.1.5.2. Secondary Estimands: Infant Participants

- **Functional antibody levels estimated by the GMT for RSV A– and RSV B–neutralizing antibody titers.**

This estimand estimates the vaccine effect in the hypothetical setting where participants follow the study schedules and protocol requirements as directed. It includes the following 4 attributes:

- Population: Infants born to maternal participants receiving 1 dose of investigational product and in compliance with key protocol criteria (evaluable participants).
- Variable: Antibody titers at birth and at 1, 2, 4, and 6 months of age.
- Intercurrent event(s): For participants who discontinue or have major protocol violations, all postdiscontinuation or postviolation observations will be censored. Results obtained from out-of-window blood draws will also be removed. Missing serology results will not be imputed, as MCAR is assumed.
- Population-level summary: GMT for RSV A– and RSV B–neutralizing antibody titers.

- **GMR estimated by the ratio of the GMT for RSV A– and RSV B–neutralizing antibody titers of the RSV vaccine group to the placebo group.**

This estimand estimates the vaccine effect in the hypothetical setting where participants follow the study schedules and protocol requirements as directed. It includes the following 4 attributes:

- Population: Infants born to maternal participants receiving 1 dose of investigational product and in compliance with key protocol criteria (evaluable participants).
- Variable: Antibody titers at birth and at 1, 2, 4, and 6 months of age.
- Intercurrent event(s): For participants who discontinue or have major protocol violations, all postdiscontinuation or postviolation observations will be censored. Results obtained from out-of-window blood draws will also be removed. Missing serology results will not be imputed, as MCAR is assumed.
- Population-level summary: GMR estimated by the ratio of the GMT for RSV A– and RSV B–neutralizing antibody titers of the RSV vaccine group to the placebo group.

CCI

CCI

CCI

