Safety – Infant	All infant participants who are born to vaccinated maternal participants. Participants will be analyzed according to the investigational product their mothers actually received. An infant born from a randomized maternal participant who did not receive investigational product will be excluded from the safety analyses.

- a. Cord blood sample must be obtained on the day of birth. If cord blood is unavailable, a venous blood sample is to be collected up to 24 hours after birth.

Major protocol violations will be determined by clinical review (through the data handling memo). A major protocol violation is a protocol violation that, in the opinion of the sponsor’s study medical monitor, would materially affect assessment of immunogenicity, eg, participant receipt of a prohibited vaccine or medication that might affect immune response or a medication error with suspected decrease in potency of the vaccine. The sponsor’s medical monitor will identify those participants with protocol violations before any immunogenicity analysis is carried out.

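### Infant titers drawn after an RSV monoclonal antibody or a transfusion stay in the main GMT and GMR analysis, because no product is prohibited for infants

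*Protocol*

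**What the plan says.** **What infants may receive.** Protocol 6.5.4 allows routine treatment and adds: "Prescription and nonprescription medications, vitamins, minerals, and herbal remedies are permitted during infant participant participation in the study". The protocol has no section on prohibited treatments for infants, and its table of contents lists none, so this is not a redaction. The only infant exclusion criterion (Protocol 5.2.2) is "Infant who is a direct descendant (eg, child or grandchild) of the study personnel". For mothers, Protocol 6.5.1 does prohibit "Blood/plasma products or immunoglobulins (except Rho(D) immune globulin".

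**What is recorded.** Protocol 6.5.5 says that details of "monoclonal antibodies (eg, Synagis), or blood transfusions (eg, whole blood, packed cells) given to the infant participant will be collected", from birth to the final study visit. The infant schedule of activities repeats this at all six visits. Neither place attaches a consequence for the titer analysis.

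**What is analysed.** The infant variable in SAP 2.1.5.2 is "Antibody titers at birth and at 1, 2, 4, and 6 months of age".

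**What removes a titer.** SAP 2.1.5.2 states: "For participants who discontinue or have major protocol violations, all postdiscontinuation or postviolation observations will be censored". Out-of-window results are also removed. SAP 6.2.2.1.1 repeats these rules for the main analysis and labels its strategy hypothetical.

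**What counts as a major violation.** SAP 4 starts from a protocol violation that, in the medical monitor's opinion, would materially affect the immunogenicity assessment. One of its examples is "participant receipt of a prohibited vaccine or medication that might affect immune response".

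**The concern.** The plan removes titers through the concept of a protocol violation. That can work for mothers, for whom antibody-containing products are prohibited. It cannot work for infants, for whom nothing is.

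The protocol's introduction describes palivizumab (Synagis) as a monoclonal antibody against the RSV F glycoprotein, and cites its effect as proof that neutralizing antibody to F protects infants. Such a product would be expected to add to the neutralizing titer being analysed. A transfusion may bring donor antibody as well. The synopsis says the infant assessments characterize antibody transferred across the placenta, and an added titer of this kind is not that.

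The later visits matter most. Protocol 4.3 says maternal antibody decays exponentially in infants, so antibody from another source forms a larger share of a 4- or 6-month titer. SAP 2 says the study will supply the data for choosing dose and formulation, so a shift in a single arm is not purely cosmetic.

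**Working it through.** **The plan's own figure.** The only sample-size figures are in Protocol Table 6. They reproduce: at a 1% true rate and 100 participants, 1 − 0.99^100 = 0.634, against the stated 0.63. They concern adverse events and do not bear on this point.

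**Following the rule for one infant.** Take an infant with a valid birth sample who receives an RSV monoclonal antibody at 3 weeks and is sampled at 1 month, in window.
1. The infant is in the evaluable set, because SAP 4 ties the sampling and assay criteria to the birth sample.
2. The infant has not discontinued, and the draw is in window.
3. The product was permitted, so there is no protocol violation and hence no major one.
4. No removal rule in SAP 2.1.5.2 or 6.2.2.1.1 applies, so the titer enters the GMT and the GMR.

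**Infants per arm and visit.** Protocol 4.1.2 gives about 500 women, or up to 650 with the southern hemisphere. There are five equal arms and two infant sampling schedules. Assuming an even split between schedules and no losses:
- 650 / 5 / 2 = 65
- 500 / 5 / 2 = 50

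Both are ceilings for their enrolment level.

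**Effect on an arm's GMT.** Titers are averaged on the log scale (SAP 5.2.2.1). If m of n infants have titers k times higher, the GMT is multiplied by k^(m/n). The documents give neither m nor k; the values below are assumptions.

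| m | k | n = 65 | n = 50 |
|---|---|---|---|
| 1 | 4 | 4^(1/65) = 1.022 | 4^(1/50) = 1.028 |
| 1 | 10 | 10^(1/65) = 1.036 | 10^(1/50) = 1.047 |
| 3 | 4 | 4^(3/65) = 1.066 | 4^(3/50) = 1.087 |
| 3 | 10 | 10^(3/65) = 1.112 | 10^(3/50) = 1.148 |

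The range is about 2% to 15%.

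**Effect on the GMR.** The multiplier is k^(f_vaccine − f_placebo), where f is the fraction affected in each arm. With 3 of 50 affected tenfold in the vaccine arm only, the GMR is multiplied by 1.15. With the same in placebo only, it is multiplied by 1 / 1.148 = 0.87. With equal fractions and fold rises it does not change.

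**Subgroups.** SAP Table 9 has four gestational-age groups. If they are even, 65 / 4 is about 16 infants per arm and visit. One infant then raises the subgroup GMT by a factor of 4^(1/16) = 1.09 to 10^(1/16) = 1.15.

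**The case against.** **Few infants will be affected.** The introduction says palivizumab is recommended only for very premature infants and others at increased risk. Mothers must have an uncomplicated singleton pregnancy, and a prior preterm delivery or signs of premature labor are listed exclusions. Infants under 1.3 kg are not bled (Protocol Table 5). This stands. Preterm infants are not excluded, however, and the protocol considered these products likely enough to ask about them at every visit.

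**The shift is within sampling error.** The documents give no SD. With an assumed SD of 0.8 to 1.2 on the natural-log scale and n = 65, the 95% CI extends by a factor of 1.22 to 1.35 on either side of a GMT. A 2% to 11% shift lies inside that, and the study is descriptive with no decision rules. This stands, and it limits the point to a cheap improvement.

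**Clinical review may catch it.** SAP 4 gives a prohibited product only as an example and leaves the decision to the medical monitor. That judgment still operates within the definition, which requires a protocol violation.

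**The estimand does not require removal.** The stated objective is to describe RSV antibody levels in these infants, and the hypothetical setting is one in which the protocol is followed. A permitted product does not breach it. This partly stands: removal is a choice. But the plan already bars blood products and immunoglobulins for mothers, and nothing shows that keeping such titers in infants was intended.

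**What a reader might infer about RSV infection.** Vaccination is timed so that infants are likely to meet RSV in their first 6 months. A reader might conclude that titers drawn after infection must also be removed. The documents do not support that. Infection is not a departure from the protocol, removing such titers conditions on a post-randomization event, and doing so would be a different estimand. The exploratory sections, where illness-related analyses would be expected, are redacted, so a related analysis cannot be ruled out.

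**Conclusion.** The gap is real but narrow. As written, the main infant analysis keeps titers drawn after a recorded RSV monoclonal antibody or transfusion, and no visible infant titer analysis in SAP 6.2.2.1 or 6.4 sets them apart. It concerns the 1-, 2-, 4- and 6-month titers. The birth sample, taken from the cord or from a vein within 24 hours, is essentially untouched.

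A reader might go further and infer that the infant titers in general cannot be read as maternal antibody. The documents do not support this. Only the affected infants' titers may include other antibody, and they are probably few.

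The 2% to 15% range for one arm's GMT rests on assumed counts (1 to 3 infants), assumed fold rises (4 to 10), an even split between schedules and no losses. It illustrates sensitivity and is not a forecast. No safety endpoint is affected, and the sample size does not change.

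**What to change.** In SAP 2.1.5.2 and 6.2.2.1.1:
- Name the infant's receipt of an RSV monoclonal antibody or a blood transfusion, and of immunoglobulin where recorded, as an intercurrent event.
- Remove that infant's later titers from the main, hypothetical-strategy analysis, and report how many are removed by arm and visit.
- Present the same GMTs and GMRs with all titers kept, as an unconditional sensitivity analysis. The mITT analysis cannot fill this role. SAP 6.2.2.1.2 runs it only if the populations differ by about 10%, and evaluable status depends on the birth sample, so removing later titers would not trigger it.

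The cost is SAP wording and one extra set of tables. There are three limits:
- A few titers are lost, probably from preterm or higher-risk infants, so they are not missing completely at random. The all-data result shows whether this matters.
- The rule needs administration dates. Protocol 6.5.5 asks for details without expressly naming dates, so the CRF should be checked.
- Immunoglobulin is not expressly listed for infants in 6.5.5 and may be captured only as medication for an adverse event.

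No change to infant treatment is implied.
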